6.6 Product Complaints

A product complaint is any complaint related to the biologic or drug component of the product or to the medical device component(s).

For a product, this may include, but is not limited to, damaged/broken product or packaging, product appearance whose color/markings do not match the labeling, labeling discrepancies/inadequacies in the labeling/instructions (e.g., printing illegible), missing components/product, device not working properly, or packaging issues.

Product complaints concerning the investigational product and/or device must be reported to AbbVie within 24 hours of the study site's knowledge of the event. Product complaints occurring during the study will be followed up to a satisfactory conclusion.

7 STATISTICAL METHODS & DETERMINATION OF SAMPLE SIZE

7.1 Statistical and Analytical Plans

Complete and specific details of the statistical analysis will be described and fully documented in the SAP. All statistical analyses will be performed using SAS version 9.4 or newer (SAS Institute Inc., Cary, North Carolina, USA).

7.2 Determination of Sample Size

Approximately 60 subjects will be enrolled into this 2-part study.

Part 1, Dose Escalation

Part 1 will enroll approximately 3 to 6 subjects per cohort using a BOIN design, resulting in a total of 6 to 12 subjects.

Part 2, Dose Expansion

Part 2 will enroll approximately 50 subjects.

Arm A: t(11;14)-Positive

The historical ORR for pomalidomide + dexamethasone is 35%.^{13,14} By adding venetoclax to this combination, an ORR of 70% is clinically meaningful for t(11;14)-positive subjects. The sample size for Arm A will be approximately 23 subjects. Allowing for a maximum 1-sided type 1 error rate of 0.025 and assuming an ORR of 35% from the historical data, 23 subjects will provide 90% power if the true ORR for t(11;14)-positive subjects treated with venetoclax + pomalidomide + dexamethasone is 70%.

Arm B: t(11;14)-Negative

The historical ORR for pomalidomide + dexamethasone is 35%. By adding venetoclax to this combination, an ORR of 60% is clinically meaningful for t(11;14)-negative subjects. The sample size for Arm B will be approximately 27 subjects. Allowing for a maximum 1-sided type 1 error rate of 0.1 and assuming an ORR of 35% from the historical data, 27 subjects will provide 90% power if the true ORR for t(11;14)-negative subjects treated with venetoclax + pomalidomide + dexamethasone is 60%.

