 - serum free-light chain (FLC) ≥ 10 mg/dL provided serum FLC ratio is abnormal
- ✓ 8. Has received at least 1 prior line of therapy.
 - A line of therapy consists of > 1 complete cycle of a single agent, a regimen consisting of a combination of several drugs, or a planned sequential therapy of various regimens
- ✓ 9. Must meet all of the following prior antimyeloma treatment parameters:
 - subject must have received at least 2 consecutive cycles of lenalidomide or a lenalidomide-containing regimen
 - subject must be refractory to lenalidomide
 - subject must have documented evidence of PD based on the investigator's determination of response as defined by the modified IMWG criteria on or after the last regimen
 - subject who received only 1 line of prior treatment must have demonstrated PD on or within 60 days of completion of the lenalidomide-containing regimen
 - subject must have been exposed to a PI alone or in combination with another agent
 - subject must have had a response of PR or better to prior therapy based on the investigator's determination of response as defined by IMWG criteria
- ✓ 10. Has t(11;14) status determined by an analytically validated fluorescent in situ hybridization (FISH) assay per central laboratory testing of a bone marrow aspirate sample and meets the following criteria:
 - For Part 1: MM subjects independent of cytogenetic profile
 - For Part 2, Arm A: subject must be t(11;14) positive
 - For Part 2, Arm B: subject must be t(11;14) negative
- ✓ 11. An Eastern Cooperative Oncology Group (ECOG) performance status ≤ 2 .

Subject History

- ✓ 12. No history of clinically significant medical conditions within the last 6 months that, in the investigator's opinion, would adversely affect the subject's participation in the study.

- ✓ 13. No history of **any active malignancies**, including myelodysplastic syndromes, within the past 3 years except for the following:

 - adequately treated in situ carcinoma of the cervix uteri or the breast;
 - basal cell carcinoma of the skin or localized squamous cell carcinoma of the skin;
 - prostate cancer Gleason Grade 6 or lower AND with stable prostate-specific antigen levels off treatment; or
 - previous malignancy with no current evidence of disease, and which was confined and surgically resected (or treated with other modalities) with curative intent and unlikely to impact survival during the duration of the study.
- ✓ 14. None of the following conditions:

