7.4 Statistical Analyses for Efficacy

Exact tests for H_0 : $ORR \leq 35\%$ and H_1 : $ORR > 35\%$ with 1-sided significance levels 0.025 and 0.1 for Arms A and B, respectively, will be performed. Point estimates and exact 95% confidence intervals of ORR for each of the 2 arms (Arms A and B) will be calculated. Details of the analysis methods for all efficacy endpoints will be provided in the SAP.

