#### 4.2 Study Design and Design Diagram

[figure not shown]
This is an open-label, multicenter study with two phases, diagrammed in [Figure 1](#).

1. **Dose escalation** will consider 6 – 12 subjects confirmed to be t(11;14)+ by an analytically-validated FISH assay per central laboratory testing before enrollment. Dose escalation will be guided by a Bayesian optimal interval (BOIN) design, based on the cumulative number of subjects who experience a DLT at the current combination dose. The subjects will be enrolled in cohorts of at least 3 subjects. The first cohort will be administered a 400 mg dose of venetoclax orally, once daily (QD). If acceptable safety and tolerability are observed at the completion of Cycle 1 in at least 3 DLT-evaluable subjects, the dose of venetoclax will be

escalated to 800 mg QD (the target dose). All subjects will be administered the approved dose of pomalidomide (oral 4 mg QD) and dexamethasone (40 mg once weekly (qw)). To be considered DLT-evaluable, subjects must complete at least 80% of pomalidomide and venetoclax dosing (or experience a DLT) during Cycle 1. DLTs are defined in the operations manual. Additional information regarding the BOIN design is provided in [Appendix A](#).

2. **Dose expansion** will consist of 2 independent arms. Arm A will consider t(11;14)+ subjects, and Arm B will consider non-t(11;14) subjects. All subjects who participate in this phase must be screened for t(11;14) translocation status before enrollment. Arm A will feature around 23 subjects and Arm B will feature around 27 subjects. All subjects will receive the ven/pom/dex combination until documented PD, unacceptable toxicity, withdrawal of consent, or they meet another criteria for discontinuation (see study protocol). Subjects may discontinue pomalidomide but continue receiving venetoclax QD for up to 2 years following the date of the last subject enrolled, provided they completed Cycle 1 of ven/pom/dex, continue to tolerate venetoclax, do not exhibit PD, and do not meet any criteria for discontinuation. AbbVie will work with the investigator to evaluate options for continued venetoclax therapy for subjects that continue to derive benefit after 2 years of treatment.

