#### 4.4 Sample Size Justification

Approximately 60 subjects will be enrolled into this two-part study. Dose escalation will enroll around 10 subjects, and dose expansion will enroll around 50 subjects.

1. **Dose Escalation** will enroll at least 3 subjects per cohort according to a BOIN design, for a total of 6 – 12 subjects.
2. **Dose Expansion** will enroll around 23 subjects in Arm A, and 27 subjects in Arm B.
  - a. Arm A: t(11;14)+: The historical ORR for pom/dex is 35%. By adding venetoclax to this combination, an ORR of 70% is clinically meaningful for t(11;14)+ subjects. Allowing for a maximum one-sided type 1 error rate of 0.025, and assuming an ORR of 35% from the historical data, 23 subjects will provide 90% power if the true ORR for t(11;14)+ subjects treated with ven/pom/dex is 70%.
  - b. Arm B: Non-t(11;14): The historical ORR for pom/dex is 35%. By adding venetoclax to this combination, an ORR of 60% is clinically meaningful for non-t(11;14) subjects. The sample size for Arm B will be approximately 27 subjects. Allowing for a maximum one-sided type 1 error rate of 0.1, and assuming an ORR of 35% from the historical data, 27 subjects will provide 90% power if the true ORR for non-t(11;14) subjects treated with ven/pom/dex is 60%.

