## 4.5 Interim Analysis

During the dose escalation phase, review meetings will be conducted at the completion of Cycle 1 in at least 3 evaluable subjects per cohort.

[figure not shown]
Since this is an open-label study, both arms of the dose-expansion phase will be continuously monitored. Interim analysis (IA) may be conducted when adequate data from approximately 10 and 16 subjects are available from Arms A and B, respectively. Figure 2 displays some guidelines for go/no-go decisions for the IA, broken down by arm. Observed ORRs in the green region may be used as evidence to accelerate studies of venetoclax in combination with IMiDs to earlier lines of therapy. Results in the yellow region suggest evaluating the depth and duration of response for more guidance.

**Arm A:** the probability of making the wrong "go" decision is 2.6%, given a true ORR of 35%, and the probability of making the wrong "no-go" decision is 1.1%, given a true ORR of 70%. The final analysis for Arm A will include the subjects from the escalation portion of the study, resulting in a grand total of around 29 t(11;14)+ subjects.

**Arm B:** the probability of making the wrong "go" decision is 2.3%, given a true ORR of 35%, and the probability of making the wrong "no-go" decision is 1.9%, given a true ORR of 60%.

The final go/no-go decision will be based on totality of efficacy and safety data.

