## 6.0 Efficacy Analyses

### 6.1 Primary Efficacy Analysis

For ORR, exact (binomial) one-sided tests of H0: ORR ≤ 35% vs H1: ORR > 35% at significance levels of 0.025 and 0.1 will be performed for Arms A and B, respectively.

Point estimates and exact (Clopper-Pearson) 95% confidence intervals of ORR for each of the two arms will be calculated.

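### Arm B has 85.5% power at 27 subjects under the planned exact test, not the stated 90%; Arm A has 88.0% at 23, and its analysis size is unsettled

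*Protocol*

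**What the plan says.** Protocol section 7.2 sizes the two expansion arms separately against a historical ORR of 35%.

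- **Arm A, t(11;14)-positive:** target ORR 70%, maximum one-sided type I error 0.025. The claim is that "23 subjects will provide 90% power if the true ORR for t(11;14)-positive subjects" is 70%.
- **Arm B, t(11;14)-negative:** target ORR 60%, maximum one-sided type I error 0.1. The claim is that "27 subjects will provide 90% power if the true ORR for t(11;14)-negative subjects" is 60%.

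Both sizes are described as approximate. SAP section 4.4 makes the same two claims.

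The test is fixed in both documents. Protocol section 7.4 plans exact tests "with 1-sided significance levels 0.025 and 0.1 for Arms A and B, respectively, will be performed". SAP section 6.1 plans "exact (binomial) one-sided tests of H0: ORR ≤ 35% vs H1: ORR > 35% at significance levels of 0.025 and 0.1".

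For Arm A, SAP section 4.5 adds that the final analysis "will include the subjects from the escalation portion of the study, resulting in a grand total of around 29 t(11;14)+ subjects". SAP section 4.2 is consistent with that, since it limits dose escalation to "subjects confirmed to be t(11;14)+ by an analytically-validated FISH assay per central laboratory testing before enrollment". Protocol section 5.1, criterion 10, says otherwise: "For Part 1: MM subjects independent of cytogenetic profile". Protocol sections 7.2 and 7.4 mention no pooling.

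**The concern.** An exact binomial test can reject only at whole numbers of responders. Its attained type I error is usually below the nominal level, and its power rises and falls in a sawtooth as n changes. A round 90% in both arms suggests a calculation that did not follow the planned test. Every input needed to check it is in the documents.

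The stated power tells readers how likely each arm is to detect the response rate called clinically meaningful. If it is overstated, a non-significant Arm B result will be read as stronger evidence against a 60% ORR than the design supports. In Arm A, the number of subjects in the test also sets the rejection threshold, so an unsettled n leaves the decision rule open.

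**Working it through.** **Inputs** (Protocol 7.2 and 7.4; SAP 4.4 and 6.1)

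- Null ORR p0 = 0.35 in both arms.
- Arm B: n = 27, p1 = 0.60, maximum one-sided alpha 0.1, stated power 90%.
- Arm A: n = 23, p1 = 0.70, maximum one-sided alpha 0.025, stated power 90%.
- Test: exact one-sided binomial, single look.

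**Method.** The critical value c is the smallest integer with P(Bin(n, 0.35) ≥ c) ≤ alpha. Power is P(Bin(n, p1) ≥ c).

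**Trying to reproduce the stated 90% for Arm B**

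The one-sample normal approximation is

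power = Φ{[(p1 − p0)√n − z·√(p0(1 − p0))] / √(p1(1 − p1))}

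= Φ{[0.25 × 5.196 − 1.2816 × 0.4770] / 0.4899} = Φ(1.404) = 92.0%.

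With a continuity correction it is 88.6%. Approximations of this kind come near 90%, but none of them is the planned test. The documents do not state how the sample size was calculated.

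**Arm B, exact test, n = 27**

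- c = 13: type I error 0.1106, above 0.1, so not allowed (power would be 92.6%).
- c = 14: type I error 0.0536, power 0.8553.

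Shortfall: 90 − 85.5 = 4.5 points. Chance of missing a true 60% ORR: 100 − 85.5 = 14.5%.

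**Arm A, exact test, n = 23**

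- c = 13: type I error 0.0283, above 0.025, so not allowed.
- c = 14: type I error 0.0100, power 0.8799.

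Shortfall: 90 − 88.0 = 2.0 points.

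**Sensitivity to n**, since both sizes are approximate:

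| Arm | n | Reject at ≥ | Attained alpha | Power |
|---|---|---|---|---|
| B | 25 | 13 | 0.060 | 84.6% |
| B | 26 | 13 | 0.083 | 89.2% |
| B | **27** | **14** | **0.054** | **85.5%** |
| B | 28 | 14 | 0.074 | 89.8% |
| B | 29 | 14 | 0.098 | 92.9% |
| A | 21 | 13 | 0.011 | 85.2% |
| A | 22 | 13 | 0.018 | 90.8% |
| A | **23** | **14** | **0.010** | **88.0%** |
| A | 24 | 14 | 0.016 | 92.6% |
| A | 25 | 15 | 0.009 | 90.2% |
| A, pooled | 29 | 16 | 0.021 | 97.1% if all have a true ORR of 70% |

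In Arm B no n from 3 to 28 reaches 90%; the highest power in that range is 89.8%, at 28. From 29 to 200 the power never falls below 90.3% (at n = 30).

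**Arm A pooling.** The 97.1% assumes that all 29 subjects are t(11;14)-positive with an ORR of 70%. The Protocol does not guarantee this for Part 1. To bound the effect, assume that all 6 escalation subjects were t(11;14)-negative and calculate P(Bin(23, 0.70) + Bin(6, p) ≥ 16):

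- p = 0.60, the Protocol's target for negative subjects: 95.0%.
- p = 0.35, the historical rate: 86.1%.

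**The case against.** The best defence is that the sizes are approximate and exact power is a sawtooth. Arm B is within one point of 90% at 26 or 28 subjects and above it at 29. Arm A is above 90% at 22 and 24, and well above it if about 29 are pooled. On this view, 27 and 23 simply fall at low points. This is a fair limit on the size of the error, and it is why the Arm A shortfall counts as slight. It does not rescue the Arm B statement, which is tied to 27 subjects.

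A second point is that the 90% may come from a normal approximation. That may explain the figure, but both documents commit to the exact test, so the figure does not describe the planned analysis.

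Third, SAP 4.5 describes the pooled subjects as t(11;14)-positive, so negative subjects may never enter the Arm A test and the 95.0% and 86.1% figures would not arise. They are bounds under a stated assumption. They become possible because SAP 4.5 includes the escalation subjects and Protocol criterion 10 no longer makes those subjects positive. The pooled total could also differ from 29, because Part 1 enrols 6 to 12.

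Fourth, both documents allow an interim analysis, and SAP 4.5 gives a 2.6% chance of a wrong go decision in Arm A. The SAP does not treat an interim go as rejecting the null hypothesis, so the final test is assessed here as a single look.

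Finally, safety is the primary objective, and the go/no-go decision rests on the totality of the data. That limits the consequence, but ORR is still the primary efficacy endpoint with a formal test in each arm.

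**Conclusion.** The stated Arm B power is wrong for the planned test: 85.5% at 27 subjects, 4.5 points below the claim, with attained one-sided type I error of 0.054. This follows from the documents' own inputs and needs no outside figure. It assumes a single final look and exactly 27 subjects.

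Arm A at 23 subjects has 88.0% power, a slight shortfall that matters less than the unsettled analysis size. The SAP (version 1.0, 06 Feb 2018) and the Protocol (synopsis dated 24 June 2020) disagree on who is in Part 1, and only the SAP pools. The Arm A threshold is 14 of 23 or 16 of 29, depending on which applies.

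The error is in the stated power only. Attained type I error is below both maxima, and the exact tests and Clopper-Pearson intervals remain valid. This should be corrected, but it does not invalidate the design.

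**What to change.** 1. In Protocol 7.2 and SAP 4.4, restate Arm B as 27 subjects, reject at 14 or more responders, attained one-sided type I error 0.054, power about 85.5%.
2. In the same places, restate Arm A at 23 subjects as reject at 14 or more, attained type I error 0.010, power about 88%.
3. Reconcile SAP 4.2 and 4.5 with Protocol criterion 10: state whether any Part 1 subjects enter the Arm A test and, if so, which ones.
4. Add a short table of critical value, attained type I error and power for the number actually treated: 25 to 29 for Arm B, and 21 to 25 for Arm A, plus the pooled total (about 29) if pooling is kept.

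The cost is the power sentences in the two documents, one table and one sentence on pooling. No extra patients are needed and the test itself is unchanged. The only downside is a slightly less favourable stated power.

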7.3 Definition for Analysis Populations

The Full Analysis Set (FAS) includes all subjects who received at least 1 dose of study drug. The FAS will be used for all safety, PK, efficacy and baseline analyses.

7.4 Statistical Analyses for Efficacy

Exact tests for H_0 : $ORR \leq 35\%$ and H_1 : $ORR > 35\%$ with 1-sided significance levels 0.025 and 0.1 for Arms A and B, respectively, will be performed. Point estimates and exact 95% confidence intervals of ORR for each of the 2 arms (Arms A and B) will be calculated. Details of the analysis methods for all efficacy endpoints will be provided in the SAP.

7.5 Statistical Analyses for Safety

Details pertaining to the safety analyses can be found in the SAP.

7.6 Statistical Analyses for Pharmacokinetics

Details pertaining to the PK analyses can be found in the SAP.

7.7 Study Interim Analysis

Interim analyses may be conducted when adequate data from approximately 10 and 16 subjects are available from Arms A and B, respectively. Details pertaining to the safety analyses can be found in the SAP.

7.8 Safety Review Committee

A Safety Review Committee (SRC) will periodically review safety data across all studies with venetoclax in MM that do not have a study-specific independent monitoring committee. This review committee will be responsible for periodic, regular reviews to assess the safety of the interventions during the study. A separate charter will be prepared outside of the protocol outlining the SRC member responsibilities, frequency of data reviews, and relevant data to be assessed.

8 ETHICS

8.1 Independent Ethics Committee/Institutional Review Board

The protocol, informed consent form(s), recruitment materials, and all participant materials will be submitted to the IEC/IRB for review and approval. Approval of both the protocol and the informed consent form(s) must be obtained before any participant is enrolled. Any amendment to the protocol will require review and approval by the IEC/IRB before the changes are implemented to the study. In addition, all changes to the consent form(s) will be IEC-/IRB-approved.

8.2 Ethical Conduct of the Study

The study will be conducted in accordance with the protocol, operations manual, International Council for Harmonisation (ICH) guidelines, applicable regulations and guidelines governing clinical study conduct, and the ethical principles that have their origin in the Declaration of Helsinki. Responsibilities of the investigator are specified in [Appendix B](#).

8.3 Subject Confidentiality

To protect subjects' confidentiality, all subjects and their associated samples will be assigned numerical study identifiers or "codes." No identifiable information will be provided to AbbVie.

9 SOURCE DOCUMENTS AND CASE REPORT FORM COMPLETION

The investigator is responsible for ensuring the accuracy, completeness, legibility, and timeliness of the data reported. All source documents should be attributable, legible, contemporaneous, original, accurate, and complete to ensure accurate interpretation of data. Clinical site monitoring is conducted to ensure that the rights and well-being of human subjects are protected, that the reported trial data are accurate, complete, and verifiable, and that the conduct of the trial is in compliance with the currently approved protocol, ICH Good Clinical Practice (GCP), and applicable local regulatory requirement(s).

10 DATA QUALITY ASSURANCE

AbbVie will ensure that the clinical trial is conducted and data are generated, documented, and reported in compliance with the protocol, ICH GCP, and applicable regulatory requirements.

11 COMPLETION OF THE STUDY

The end-of-study is defined as the date of the last subject's last visit or date of the last follow-up contact, whichever is later.

APPENDIX A. STUDY SPECIFIC ABBREVIATIONS AND TERMS

Abbreviation	Definition
AE	adverse event
ALT	alanine aminotransferase
AML	acute myeloid leukemia
ANC	absolute neutrophil count
aPTT	activated partial thromboplastin time
AST	aspartate aminotransferase
AUC	area under the plasma concentration versus time curve (AUC)
AUC ₀₋₂₄	AUC from time 0 to 24 hours postdose
BCL	B-cell lymphoma
BCL-w	B-cell lymphoma-Walter and Eliza Hall Institute
BCL-X _L	B-cell lymphoma – extra large
BCRP	breast cancer resistance protein
BOIN	Bayesian optimal interval
CDK	cyclin-dependent kinase
CLL	chronic lymphocytic leukemia
C _{max}	maximum concentration
CR	complete remission
CrCL	creatinine clearance
CRF	Case Report Form
CRI	complete remission with incomplete blood count recovery
CT	computed tomography
CTCAE	Common Terminology Criteria for Adverse Events
CYP	cytochrome P450
DLT	dose-limiting toxicity
DNA	deoxyribonucleic acid
DOR	duration of response
ECG	electrocardiogram
ECOG	Eastern Cooperative Oncology Group
eCRF	electronic case report form
FAS	Full Analysis Set

FFPE	fixed formalin paraffin embedded
FISH	fluorescent in situ hybridization
FLC	free-light chain
GCP	Good Clinical Practice
G-CSF	granulocyte-colony stimulating factor
HBsAg	hepatitis B surface antigen
HCV	hepatitis C virus
HDAC	histone deacetylase
HR	hazard ratio
ICH	International Council for Harmonisation
IEC	Independent Ethics Committee
Ig	immunoglobulin
IHC	immunohistochemistry
IMiD	immunomodulatory drug
IMWG	International Myeloma Working Group
INR	international normalized ratio
IRB	Institutional Review Board
IRT	Interactive Response Technology
IV	intravenous
IVIG	intravenous immunoglobulin
K_i	inhibition rate constant
MCL	myeloid-cell leukemia
MM	multiple myeloma
M-protein	monoclonal-protein
MR	minimal response
MRD	minimal residual disease
MRI	magnetic resonance imaging
NCI	National Cancer Institute
NHL	non-Hodgkin's lymphoma
OATP	organic anion-transporting polypeptide
ORR	overall response rate
OS	overall survival
PD	progressive disease
PET	positron emission tomography

PFS	progression-free survival
P-gp	P-glycoprotein
PI	proteasome inhibitor
PK	pharmacokinetic(s)
PO	oral
POEMS	polyneuropathy, organomegaly, endocrinopathy, monoclonal gammopathy, and skin changes
PR	partial response
PT	prothrombin time
QD	once daily
qPCR	quantitative polymerase chain reaction
qw	once weekly
REMS	risk evaluation and mitigation strategies
RNA	ribonucleic acid
R/R	relapsed or refractory
SAE	serious adverse event
SAP	Statistical Analysis Plan
sCR	stringent complete response
SD	stable disease
SLL	small lymphocytic lymphoma
SRC	Safety Review Committee
SUSAR	Suspected Unexpected Serious Adverse Reaction
TA MD	Therapeutic Area Medical Director
TLS	tumor lysis syndrome
T _{max}	time to maximum concentration
TTP	time-to-progression
ULN	upper limit of normal
VGPR	very good partial response

